## 6.2 ***Methods and timelines for the assessment of efficacy endpoints***

Retrospective (2 years before ICF signing) and prospective (1 year after ICF signing) collection of observational data from UC/CD patients.

# 7 SAFETY AND EXPLORATORY ASSESSMENTS

## 7.1 ***Safety endpoints (outcomes):***

- Patient incidence and type of adverse drug reactions related to IBD treatment occurring during 12-months treatment period within routine clinical practice by treatment type (biologics or non-biological therapy) and treatment history (biologic treatment naïve or with prior biological treatment);
- Patient incidence and type of serious adverse events related to IBD treatment occurring during 12-months treatment period within routine clinical practice by treatment type (biologics or non-biological therapy) and treatment history (biologic treatment naïve or with prior biological treatment).

## 7.2 ***Methods and timelines for the assessment of safety endpoints***

Start of AEs and ADRs collection: AEs/ADRs must be collected from the date after ICF signing. Routine collection of AEs/ADRs will continue until Final visit (Visit 3).

A physician must report all reportable AEs and ARDs on the special “AE reporting form” provided by the Sponsor. The physician should record only one AE per 1 “AE reporting form”. The physician has to record the diagnosis if available. If no diagnosis is available, the physician should record each sign and symptom as separate reports

## 7.3 ***Exploratory endpoints:***

- Number of moderate to severe UC and CD patients with TB positive tests results/active TB before start of biological therapy.
- Number of moderate to severe UC and CD patients with TB reactivation/occurrence in frames of this study by treatment type (biologics or/and non-biological treatment).

Protocol ID	MACS-2017-102279	STATISTICAL ANALYSIS PLAN	Page 17 of 41	
IP	N/A		Date	30.12.2021
ID	MACS-2017-102279_SAP		Version	v1.2 final

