11.1 Inclusion Criteria

Every eligible patient at participating investigational sites must meet the following criteria:

Inclusion criteria:

1. Male and female patients 18 years or older by the time of enrolment
2. Confirmed diagnosis of Crohn's disease or ulcerative colitis for at least 2 years prior to enrolment in the study.
3. The presence of a moderate to severe IBD flare at the time of enrolment or in patient anamnesis within 2 years before enrollment treated with steroids or/ and immunosuppressive agents or/ and biologic therapy. IBD flare(s) must be confirmed in the source documentation.
4. Current treatment with steroids or/ and immunosuppressive agents or/ and 5-ASA or/ and biologic therapy
5. Written informed consent, signed before the participation in the study begins.

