12.2 Tabulated overview of data collection

The documentation of study data will be reported by investigators via electronic case report form (eCRF).

Assessment / Procedure	Retrospective data collection*	Baseline visit (V1, Day 1)	Observational visit (V2, Month 6)	Final visit (V3, Month12)
Informed consent		X		
Patients' eligibility assessment: Inclusion/exclusion criteria		X		
Date of visit		X	X	X
Demographics data		X		
Disability		X		
Physical examination		X	X	X
Medical history / Concurrent medical conditions	X	X		
History of IBD	X	X		
IBD family history		X		
IBD assessment	X	X	X	X
Disease activity data		X	X	X
IBD status		X	X	X
Laboratory and instrumental evaluation of IBD **	X	X	X	X
IBD treatment	X	X	X	X
Healthcare resources utilization	X	X	X	X
Concomitant treatment		X	X	X
Physician Survey		X		X
Adverse events			X	X

* Retrospective data within two years before of patient enrolment in the study will be collected at Visit 1 after the signing of the informed consent form

**All examinations (laboratory tests and instrumental exams) are done in accordance with clinical routine practice and physician's decision. All examinations results should be registered in electronic CRF only if they are done in routine practice.

12.3 Data collected on the Baseline visit (V1), including collection of Retrospective data within two years before of patient enrolment in the study

The baseline visit takes place at the physician's office. Data to be collected:

- Date of Informed consent form signing (day, month, year);
- Inclusion/exclusion criteria;
- Date of visit (day, month, year);
- Demographics data (gender, date of birth, ethnicity, region of residence, smoking status, employment status (employed, unemployed, retired, student, other));
- Disability:
 - Disability group
 - Cause of disability
 - Year of disability
- Physical examination: height (cm) and weight (kg), body mass index calculation;
- Medical history/Concurrent medical conditions (disease, date of diagnosis, resolution date);
- History of inflammatory bowel disease (IBD):
 - Type of inflammatory bowel disease (ulcerative colitis (UC) or Crohn's disease (CD)),
 - Date of IBD diagnosis,
 - Date of IBD symptoms onset,
 - Availability of observation in the current investigational site within previous 2 years
- IBD family history (degree of relationship);
- Clinical course of IBD (acute, chronic continuous, chronic recurrent);
- IBD assessment for the last 2 years and at the time of the baseline visit:

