12.7 Laboratory and instrumental examinations to be documented in the study

All examinations (physical examination and vital signs, laboratory tests and other exams) will be performed in accordance with common clinical routine practice, routine practice of a particular medical institution. All examinations are solely based on the physician's decision about strategy of diagnostics and treatment.

The following laboratory and instrumental examinations are planned to collect in the study:

- Laboratory tests results
 - Biomarkers: CRP, faecal calprotectin
 - Immunological tests: TB diagnostic test
- Endoscopic examination/ biopsy of GI tract
- X-ray of GI tract and lungs
- MRI/CT examination related to IBD
- Ultrasound examination related to IBD

All laboratory and instrumental examinations are collected during all period of data collection: retrospectively, at Baseline visit, through 1 year of prospective observation.

12.8 Documentation of Medical history and Concurrent Medical Conditions.

Medical history is history of diseases indicated before signing of the Informed Consent Form.

Concurrent medical conditions are those significant (ongoing conditions or diseases that are present at signing of informed consent). Concurrent medical conditions may include not limited to tuberculosis, cardiovascular disorders, diabetes, chronic pulmonary artery disease, chronic kidney disease. The condition (i.e., diagnosis) should be registered in eCRF.

Time of medical event/disease	How it should be documented
Before ICF signed	Medical history
At the moment of ICF signing	Concurrent medical conditions
After ICF signing	Adverse Events

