- Laboratory and instrumental evaluation of IBD for the last 2 years and at the time of the baseline visit (if done within routine practice);
- IBD treatment:
  - IBD treatment for the last 2 years and at the time of the baseline visit;
  - IBD surgical treatment for the last 2 years and at the time of the baseline visit;
- Healthcare resources utilization for the last 2 years and at the time of the baseline visit;
- Concomitant treatment.

Protocol ID	MACS-2017-102279	STATISTICAL ANALYSIS PLAN	Page 12 of 41	
IP	N/A		Date	30.12.2021
ID	MACS-2017-102279_SAP		Version	v1.2 final

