## 7.4 Subgroup analysis:

### Criteria for the treatment of inflammatory bowel diseases

1. Depending on the conditions of prescribing biological therapy:
  - a. By the period of time from diagnosis to biological therapy prescription:
    - up to 2 years inclusive
    - from 2 to 5 years inclusive
    - more than 5 years
  - b. By the number of courses of systemic corticosteroids in medical history before biological therapy prescription:
    - < 3 courses
    - ≥ 3 courses
2. Patients not assigned to biological therapy:
  - a. By the period of time from diagnosis to biological therapy prescription:
    - up to 2 years inclusive
    - from 2 to 5 years inclusive
    - more than 5 years
  - b. By the number of courses of systemic corticosteroids in medical history before biological therapy prescription:
    - < 3 courses
    - ≥ 3 courses

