#### 8.1.3 Assessment of secondary and exploratory endpoints

**Each original treatment combination** (defined as the treatment combination that was used by the patient at the very start of retrospective observation period, i.e. first recorded treatment combination in the study) will be tabulated by the below listed parameters using the generic table format below (see example tables: Table 10, Table 11, Table 12 and Table 6):

- Demographic data;
- Disease activity at Visits 1, 2, 3 (Mayo, Harvey-Bradshaw indices);
- Disease status assessed by investigator at Visits 1, 2, 3;
- Frequency (percentage) of clinical, endoscopic and histologic remission at Visits 1, 2, 3 and retrospective period of observation;
- Extent of lesion at Visits 1, 2, 3;
- Systemic (extraintestinal) manifestations at Visits 1, 2, 3;
- Total number, duration and severity of disease exacerbations by Visit 1, 2 and 3;
- Total number, type and duration of disease complications by Visit 1, 2 and 3;
- Laboratory and instrumental assessments at Visits 1, 2, 3;
- Percentage of patient with surgical treatment by Visits 1, 2, 3 grouped by:
  - Indication;
  - Surgery type;
  - Presence of complications.
- Number of surgeries by Visits 1, 2, 3;

Protocol ID	MACS-2017-102279	STATISTICAL ANALYSIS PLAN	Page 25 of 41	
IP	N/A		Date	30.12.2021
ID	MACS-2017-102279_SAP		Version	v1.2 final

- Percentage of patients with at least one episode of failure or biological or/and non-biological therapy (e.g., dose escalation of biologics, switching to another therapy, IBD-related surgery, medication augmentation) by Visits 1, 2 and 3;
- Separately for patients who achieved / not achieved T2T treatment goals (based on the clinical assessment of IBD) by Visits 1, 2 and 3:
  - Presence of therapeutic de-escalation;
  - Presence of therapeutic escalation;
  - Continuation of therapy without any changes.
- Healthcare resources utilization:
  - Hospitalizations due to complications;
  - IBD-related surgeries;
  - Percentage of patients that used healthcare resources;
- Only for biological therapy - percentage (by Visits 1, 2, 3) of patients with:
  - Positive test results for TB before the start of biological therapy;
  - Active TB before the start of biological therapy;
- Percentage of patients by Visits 1, 2, 3 with:
  - Reactivation of TB;
  - New occurrence of TB.

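### The number of patients with a positive TB test before a biologic will be too low, because TB tests are collected only from two years before enrolment while biologics may have started earlier

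*SAP*

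**What the plan says.** Protocol 6.2 and SAP 7.3 define the first TB outcome as the "Number of moderate to severe UC and CD patients with TB positive tests results/active TB before start of biological therapy". SAP 8.1.3 splits it, for biological therapy only, into two percentages by Visits 1, 2 and 3. One is "Positive test results for TB before the start of biological therapy"; the other is active TB before that start. Both are tabulated by original treatment combination, meaning the first one recorded, in use when the retrospective period opens.

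Protocol 12.7 lists "Immunological tests: TB diagnostic test" among the laboratory items and adds: "All laboratory and instrumental examinations are collected during all period of data collection: retrospectively, at Baseline visit, through 1 year of prospective observation". The retrospective part is limited in the footnote to the schedule in Protocol 12.2: "Retrospective data within two years before of patient enrolment in the study will be collected at Visit 1". SAP 5.3.1 repeats the limit for this data set: "Laboratory and instrumental evaluation of IBD for the last 2 years and at the time of the baseline visit (if done within routine practice".

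On timing of treatment, Protocol 11.1 requires a diagnosis of Crohn's disease or "ulcerative colitis for at least 2 years prior to enrolment in the study" and accepts current biologic treatment. Neither 11.1 nor 11.2 restricts when the biologic began. SAP 7.4 forms subgroups "By the period of time from diagnosis to biological therapy prescription", the first being two years or less.

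On denominators, SAP 8.1.1 and Protocol 15.2.1 base percentages on non-missing observations. SAP 8.4 plans neither imputation nor an assessment of the missing-data pattern.

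**The concern.** The outcome asks about the patient's state before the biologic began, but the test data are bounded by the enrolment date. For anyone who started a biologic more than two years before Visit 1, the two do not overlap: the pre-start test falls outside the window, and any test inside it was taken after that start. The SAP gives no rule for these patients and no category for them.

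Assessing TB is the protocol's only exploratory objective. A count that depends on how long patients had already been treated cannot be read as the frequency of positive TB tests before biologic treatment. The choice of table columns adds to this. Patients placed in a biologic column by the combination they were taking when the window opened are largely those whose pre-start test lies outside it.

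**Working it through.** **Are earlier starts possible, and foreseen?** Diagnosis is at least two years old with no upper limit, and the biologic start is not limited. SAP 7.4 has a stratum for a biologic prescribed within two years of diagnosis. A patient in that stratum who was diagnosed more than four years before enrolment started the biologic more than 4 − 2 = 2 years before enrolment, so before the window. The plan therefore expects patients of a kind for whom the pre-start test is not collected.

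**The plan's own figures.** The documents state no figure for the TB outcome. The planning figures in Protocol 15.4 reproduce:

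- Crohn's disease patients on biologics: 2000 × 0.40 × 0.40 = 320; after 10% drop-out, 320 × 0.90 = 288.
- 95% interval at a 50% failure rate: 0.50 ± 1.96 × √(0.25/288) = 0.50 ± 0.058, or 44.2% to 55.8%, as stated.
- All patients on biologics: 2000 × 0.40 = 800 (320 Crohn's disease and 480 ulcerative colitis).

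**Effect on the TB test line.** Let B = 800. Let p be the share who were test-positive before the biologic, and f the share who started before the window. Neither p nor f is in the documents; both are assumed. The calculation takes p to be the same in earlier and later starters, and every in-window starter to have a pre-start test on record.

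- Positives captured = B × p × (1 − f)
- Positives missed = B × p × f
- Percentage over all B = p × (1 − f)
- Percentage over patients with a captured pre-start test = p

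At p = 10% there are 800 × 0.10 = 80 positives:

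| Assumed f | Captured | Missed | Over all 800 | Over those captured |
|---|---|---|---|---|
| 10% | 72 | 8 | 9.0% | 10% of 720 |
| 25% | 60 | 20 | 7.5% | 10% of 600 |
| 50% | 40 | 40 | 5.0% | 10% of 400 |

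For p from 5% to 20% and f from 10% to 50%, the number missed runs from 800 × 0.05 × 0.10 = 4 to 800 × 0.20 × 0.50 = 80.

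The count falls by the factor (1 − f) whatever denominator is used. The percentage falls only if earlier starters remain in the denominator.

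**The case against.** A reader might infer that the plan counts every patient without a captured pre-start test as negative. The documents do not say so. Percentages use non-missing observations and missing data are not imputed. If the missing-data rule is applied strictly to pre-start tests, and positivity is the same in both groups, the percentage does not fall. This stands, so a biased percentage is a possibility and not a stated feature of the plan. It does not rescue the count. Nor does it tell the reader which patients the percentage describes: SAP section 2 defines N as all patients in the group, and SAP 8.1.4 annotates tables with totals that include missing observations.

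A second tempting reading is that the whole outcome is lost for earlier starters. That also goes too far. Active TB is a separate line in SAP 8.1.3, and past disease can enter through medical history with diagnosis and resolution dates (Protocol 12.3). The definition in Protocol 12.8 carries no two-year limit, although the schedule marks that row in the retrospective column too. The shortfall concerns test results.

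Third, the documents do not say that the start of biological therapy means the first biologic. If it meant the start of any observed course, a test taken before a switch inside the window would qualify. This is fair, and it shows that the index date needs defining.

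Finally, the outcome is exploratory and descriptive. The primary outcome and the sample size are untouched.

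**Conclusion.** The concern holds for the test-based part of the outcome, with the start of biological therapy read as the start of the first biologic. TB tests reach back two years, biologics may have started earlier, and nothing in the SAP makes the gap visible. The number of patients with a positive pre-start test is too low as defined. The percentage is either too low or refers to an unlabelled subset, depending on a denominator choice that the SAP leaves open.

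The size cannot be computed from the documents. The loss of 8 to 40 of 80 positives rests on the planned 800 biologic patients, an assumed 10% positivity and an assumed 10% to 50% of earlier starters. It should be read as an illustration. The point warrants a change to the SAP, but it bears only on how an exploratory result is reported.

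**What to change.** In SAP 7.3 and 8.1.3:

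- Define the index date as the start of the patient's first biologic. Any known earlier biologic use makes the patient an earlier starter, so that the first biologic recorded in the window is not mistaken for the first one taken.
- Report the TB-test line only for patients whose index date falls inside the data window (24 months before to 12 months after Visit 1) and who have a TB test dated before it. Give positive and negative with that denominator.
- Show earlier starters, and in-window starters without a pre-start test, as *not assessable*, with their numbers.
- Report active TB before the biologic as its own line from medical history dates, without requiring a test, and state how far back that history reaches.
- Do not use tests dated after the index date as pre-start results. List them separately and not under the second TB outcome, since a positive test is not in itself reactivation or occurrence.

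The cost is SAP wording, one date comparison and a smaller denominator. The database must hold TB test dates and biologic start dates. Protocol 12.6.1 lists a start date for biologics, and the SAP 7.4 subgroups need one in any case. Protocol 12.7 lists test results without mentioning dates, so their availability should be confirmed first.

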## 7.4 Subgroup analysis:

### Criteria for the treatment of inflammatory bowel diseases

1. Depending on the conditions of prescribing biological therapy:
  - a. By the period of time from diagnosis to biological therapy prescription:
    - up to 2 years inclusive
    - from 2 to 5 years inclusive
    - more than 5 years
  - b. By the number of courses of systemic corticosteroids in medical history before biological therapy prescription:
    - < 3 courses
    - ≥ 3 courses
2. Patients not assigned to biological therapy:
  - a. By the period of time from diagnosis to biological therapy prescription:
    - up to 2 years inclusive
    - from 2 to 5 years inclusive
    - more than 5 years
  - b. By the number of courses of systemic corticosteroids in medical history before biological therapy prescription:
    - < 3 courses
    - ≥ 3 courses

### Subgroups of first-line biological therapy

1. Vedolizumab
  - a. By the period of time from diagnosis to biological therapy prescription:
    - up to 2 years inclusive
    - from 2 to 5 years inclusive
    - more than 5 years
  - b. By the number of courses of systemic corticosteroids in medical history before biological therapy prescription:
    - < 3 courses
    - ≥ 3 courses

Protocol ID	MACS-2017-102279	STATISTICAL ANALYSIS PLAN	Page 18 of 41	
IP	N/A		Date	30.12.2021
ID	MACS-2017-102279_SAP		Version	v1.2 final

c. Depending on disease activity at the moment of biological therapy prescription:

- Crohn's disease, the Harvey-Bradshaw index:

- < 5 points
- 5-16 points
- >16 points

- Ulcerative colitis, the Partial Mayo Score:

- 0 scores
- 1-2 scores
- 3-5 scores
- ≥ 6 scores

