14.1.3. Protocol Deviations

The investigator should not deviate from the protocol, except where necessary to eliminate an immediate hazard to study patients. In accordance with NIS definition all examinations and other data should be registered in the CRF only if they are done in routine practice.

Should other unexpected circumstances arise that will require deviation from protocol-specified procedures and data collections rules, the investigator should consult with the Sponsor, responsible CRO or designee (and IRB or IEC, as required) to determine the appropriate course of action. There will be no exemptions (a prospectively approved deviation) from the inclusion or exclusion criteria.

In the event of a significant deviation, the site should notify the sponsor or its designee (and IRB or EC, as required). Significant deviations include, but are not limited to, those that involve fraud or misconduct, or confound interpretation of primary study assessment.

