#### Exploratory objectives:

- To assess TB in moderate to severe IBD patients receiving biologics and/or non-biological treatment.

Protocol ID	MACS-2017-102279	STATISTICAL ANALYSIS PLAN	Page 8 of 41	
IP	N/A		Date	30.12.2021
ID	MACS-2017-102279_SAP		Version	v1.2 final

- To describe disease activity parameters, quality of life indicators, clinical outcomes, and safety criteria in different subgroups of patients.

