### **8.6 Analysis populations (data sets)**

Due to observational nature of this study patients will not be excluded from analysis based on their performance and/or data availability. All obtained data will be summarized after data base cleaning and lock.

All planned analyses (including descriptive analyses and study listings) will be performed for Full Analysis Set (FAS) of data.

The following patient's populations will be included into statistical analysis:

- **All Patients Enrolled population (equal to FAS):** All patients who signed informed consent to enter the study.

*Subjects that were enrolled with the violation of inclusion and subsequently withdrawn from the study (upon recognition of such violation) will be excluded from FAS and analyzed separately for baseline characteristics only (the decision whether to analyze such patients in the interim analysis will be defined by the number of such patients – summary data will be presented if this subgroup is >10 observations).*

- **Safety population:** Patients who have taken at least one dose of any IBD medicine after enrolling in the study (Baseline visit).

Due to observational nature of the study, and possible presence of missing data for analysis, it is possible to exclude several patients or the entire study center at the analysis stage.

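### SAP 7.4: no eligible patient in the earliest time-from-diagnosis stratum can start a first biologic after enrolment, so the strata differ in time since start by design

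*SAP*

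**What the plan says.** - **The strata.** SAP 7.4 item 1 ("Depending on the conditions of prescribing biological therapy") and each of the four first-line drug blocks classify patients "By the period of time from diagnosis to biological therapy prescription". The categories are "up to 2 years inclusive", "from 2 to 5 years inclusive", and over 5 years.
- **Eligibility.** Protocol 11.1 criterion 2 requires "Confirmed diagnosis of Crohn's disease or ulcerative colitis for at least 2 years prior to enrolment in the study". Criterion 4 accepts current treatment with steroids, immunosuppressants or 5-ASA alone, so a biologic need not be in use at entry. Protocol 14.1.3 adds: "There will be no exemptions (a prospectively approved deviation) from the inclusion or exclusion criteria".
- **Use of the strata.** The SAP 4.2 exploratory objective is "To describe disease activity parameters, quality of life indicators, clinical outcomes, and safety criteria in different subgroups of patients".
- **The clock.** SAP 8.1.3 tabulates activity, remission, surgery and treatment failure at or by Visits 1, 2 and 3. SAP 8.1.5 states that safety collection begins at consent, with no retrospective safety data.
- **What is absent.** SAP 7.4 does not align patients on biologic start, restrict to new users or split by time since start. SAP 8.1.2 summarises course duration and total duration of use, but by treatment combination and not within these strata.

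**The concern.** A table of outcomes by time from diagnosis to biologic will be read as early versus late prescription. That reading needs the strata to be observed over comparable parts of the biologic course. Here the variable that defines the strata, together with the entry rule, fixes which parts can be observed.

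The early stratum can contain only patients who had started by enrolment. The later strata can mix established users, recent starters and patients who start after Visit 1. A difference in adverse reactions, failure or remission can then arise from the observation window alone.

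**Working it through.** **Inputs.** Let D be years from diagnosis to enrolment and L years from diagnosis to first biologic, reading prescription as start. The documents give D ≥ 2 (Protocol 11.1), L ≤ 2 for the early stratum (SAP 7.4), and an observed window from 2 years before enrolment to 1 year after (Protocol 10.3). They do not give the distributions of D or L. The plan has no figure of its own on this point to reproduce.

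**Step 1: who can start after enrolment.** Start relative to enrolment is L − D.
- Early stratum: L ≤ 2 and D ≥ 2, so L − D ≤ 0. The latest possible start is the enrolment day, when D = L = 2.
- 2 to 5 years: D = 2.5 and L = 3 gives a start 0.5 years after enrolment.
- Over 5 years: D = 7 and L = 7.5 also gives 0.5 years after.

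Time since start at Month 12 is 1 + D − L. It is at least 1 year in the early stratum and can be close to 0 in the others.

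**Step 2: safety.** Events are collected only from consent. A reaction soon after the first biologic dose can be recorded prospectively for a patient who starts after Visit 1. In the early stratum it can be recorded only if the start fell at or just before enrolment.

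**Step 3: how far the strata differ (assumed inputs).** D was taken as uniform on 2–6, 2–10 or 2–20 years, or as 2 + exponential with mean 5. Starts occurred at 0.1 or 0.3 per year, or evenly over the window. Counting starts inside the window only:

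| | Up to 2 y | 2–5 y | Over 5 y |
|---|---|---|---|
| Start after enrolment | 0% | 28–34% | 34–75% |
| Mean years since start, Visit 1 | 1.3–1.4 | 0.6–0.7 | 0.1–0.7 |
| Mean years since start, Month 12 | 2.3–2.4 | 1.5–1.6 | 0.7–1.5 |

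In the start-rate scenarios with all earlier starts counted, the shares starting after enrolment are 0%, 4–24% and 8–74%.

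**Step 4: effect on failure (assumed inputs).** Take D = 2 + exponential with mean 6, L exponential with mean 6, and starts from 24 months before to 12 months after enrolment. Failure is 40% in the first year on drug and 15% per year after, the same in every stratum. Three patients show the mechanism:
- Start 1.33 years before Visit 1: failure after Visit 1 is 15%; from start to Month 12 it is 1 − 0.60 × 0.85^1.33 = 52%.
- Start 0.5 years before Visit 1: after Visit 1, 1 − 0.60^0.5 × 0.85^0.5 = 29%; from start, 1 − 0.60 × 0.85^0.5 = 45%.
- Start 0.5 years after Visit 1: 1 − 0.60^0.5 = 23% on either count.

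Averaged by simulation:

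| | Up to 2 y | 2–5 y | Over 5 y |
|---|---|---|---|
| Start after Visit 1 | 0% | 33% | 39% |
| Failure counted after Visit 1 | 17.2% | 22.6% | 21.9% |
| Failure counted from biologic start to Month 12 | 51.6% | 40.1% | 37.7% |

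Counted after Visit 1, the early stratum looks better by 22.6 − 17.2 = 5.4 and 21.9 − 17.2 = 4.7 points. Counted from biologic start, it looks worse by 51.6 − 40.1 = 11.5 and 51.6 − 37.7 = 13.9 points. If starts before the 24-month window are also included, the gap after Visit 1 shrinks to 2–4 points.

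**Step 5: which count the plan uses.** SAP 8.1.3 counts patients with at least one failure by each visit and gives no starting point, which reads as cumulative. The sample-size text (Protocol 15.4, SAP 8.2) speaks of failure during the 12 months of observation. Both readings are open.

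**The case against.** A reader might infer that early prescription is bound to look better. Giving the full 12-month 40% risk to everyone under 6 months on drug at Visit 1 or starting later, and 15% to the rest, yields 16.5%, 27.8% and 29.0%, gaps of 11.3 and 12.5 points. The documents do not support this. Patients who start after Visit 1 have less than 12 months on drug by Month 12, and allowing for that reduces the gap to about 5 points. On the cumulative reading of SAP 8.1.3 the sign reverses.

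Other objections stand in part:
- **Criterion 3** requires a moderate to severe flare at enrolment or in the previous 2 years. Anyone who started a biologic more than 2 years before enrolment must have flared since, which removes sustained responders and works against an early advantage.
- **Started does not mean still taking.** Patients may have stopped or switched, so the quantity is time since first biologic. It is also not longer for every early patient: D = 2.5, L = 1.5 gives 1 year at Visit 1, while D = 15, L = 6 gives 9. The early mean was longest in every scenario tried.
- **SAP 7.4 gives no classification date.** That the later strata include starters after Visit 1 is inferred from the entry criteria.
- **The study is descriptive.** Protocol 15.2.4 disclaims full evaluation of effectiveness and SAP 8.3 plans no tests. This limits the damage but does not make the strata comparable, and SAP 8.1.1 still foresees exploratory association analyses.
- **Cells are thin.** With 40% of 2000 on biologics, 800 patients over 4 drugs × 2 diseases × 3 strata average 33 per cell. Splitting every drug block at Visit 1 leaves 5 non-empty cells per drug and disease, averaging 800 / 40 = 20. This is a sound reason to confine the split to the pooled table.

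**Conclusion.** The structural point is exact for eligible patients: no one in the early stratum can start a first biologic after enrolment. The one exception is a patient who violated inclusion and stayed in, because SAP 8.6 removes from the full analysis set only "Subjects that were enrolled with the violation of inclusion and subsequently withdrawn from the study".

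The firmest consequence is for safety, where reactions soon after a first biologic are almost unobservable in the early stratum. Failure and remission comparisons mix different exposure periods, and for failure even the direction of the artefact depends on where counting begins. The point estimates in step 4 rest on assumed failure rates, disease durations and start times. They show that the artefact can matter and can change sign; they do not predict its size. The issue affects interpretation of exploratory tables, not the primary description of treatment patterns, and should be corrected.

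**What to change.** - **SAP 7.4 item 1a** (all first-line biologics pooled, UC and CD separately): tabulate outcomes and safety by stratum in two tables, one for first biologics started on or before Visit 1 and one for those started after it. State that the early stratum is empty by design in the second.
- Report time since first biologic at Visit 1 for each stratum.
- State whether failure is counted from biologic start or from Visit 1.
- **Four drug blocks:** report only time since first biologic and the number of starters after Visit 1 per stratum.

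**Cost.** SAP wording and one table split. Visit, diagnosis and biologic start dates are already collected (Protocol 12.3, 12.6.1). Cells in the pooled table become smaller. On the protocol's assumptions there are 320 CD and 2000 × 0.4 × 0.6 = 480 UC patients on biologics, so five non-empty cells would average 64 and 96 before drop-out if evenly filled. The cells for starts after Visit 1 may well be smaller than that.
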